11.5 Safety signal detection

Selected data from this study will be reviewed periodically to detect as early as possible any safety concern(s) related to the IMP so that investigators, clinical study subjects, regulatory authorities, and IRBs/IECs will be informed appropriately and as early as possible.

The Study Physician or medically qualified designee/equivalent will conduct an ongoing review of SAEs and perform ongoing SAE reconciliations in collaboration with the PS representative.

As appropriate for the stage of development and accumulated experience with the IMP, medically qualified personnel at UCB may identify additional safety measures (eg, AEs, vital signs, laboratory or ECG results) for which data will be periodically reviewed during the course of the study.

11.6 Laboratory measurements

A central laboratory will perform routine hematology, clinical chemistry, and hormone analyses.

It is recommended that subjects be scheduled for morning appointments to complete these procedures. However, if morning appointments are not feasible, then subjects should continue to be scheduled at approximately the same time of day as all other visits.

Treatment of the venous puncture or indwelling venous catheter site with a topical anesthetic (eg, EMLA) prior to the needle stick is permissible.

Urinalyses are performed locally using urine dipsticks. If the dipstick results are abnormal and of clinical concern, a repeat sample will be sent to the central laboratory for evaluation.

The laboratory parameters listed in [Table 11–2](#) will be measured.

Table 11–2: Laboratory measurements

Hematology	Endocrine	Urinalysis
Red blood cell count	Estradiol ^a	Color
Hematocrit	FSH	Appearance
Hemoglobin	IGF-1	Glucose
Platelet count	LH	Protein
White blood cell count ^b	Progesterone ^a	Blood
RBC indices	Prolactin	Ketones
MCH	Testosterone ^c	Pregnancy test ^a
MCV	T3	
MCHC	T4	
RDW	TSH	
Chemistry		
ALT	Glucose	
AST	Phosphorus	
Albumin	LDH	
Alkaline phosphatase	Potassium	
Bicarbonate	Serum iron	
BUN	Sodium	
Calcium	Total cholesterol	
Chloride	Total bilirubin	
Creatinine	Total protein	
Ferritin	Transferrin	
GGT	Uric acid	

ALT=alanine aminotransferase; AST=aspartate aminotransferase; BUN=blood urea nitrogen; FSH=follicle-stimulating hormone; GGT=gamma-glutamyl transferase; IGF-1=insulin-like growth factor-1; LDH=lactate dehydrogenase; LH=luteinizing hormone; MCH=mean corpuscular hemoglobin; MCHC= mean corpuscular hemoglobin concentration; MCV=mean cell volume; RBC=red blood cell; RDW=red cell distribution width; T3=triiodothyronine; T4=thyroxine; TSH=thyroid-stimulating hormone

^a Females only. Serum pregnancy test at Screening and urine pregnancy test at all other visits. A positive urine pregnancy test must be confirmed by a serum pregnancy test.

^b With differential.

^c Males only.

11.6.1 Evaluation of PDILI

The PDILI IMP discontinuation criteria for this study are provided in [Section 6.3.1](#), with the accompanying required follow-up investigation and monitoring detailed below. All PDILI events must be reported as an AE and reported to the study site and sponsor within 24 hours of learning of their occurrence. Any PDILI event that meets the criterion for potential Hy's Law must be reported as an AE of special interest (see [Section 11.1.1.3](#)), and, if applicable, also reported as an SAE (see [Section 11.1.1.2](#)).

Evaluation of PDILI consists of the diagnostic testing and continued monitoring included in [Table 11-3](#) (specific tests dependent on laboratory results and corresponding symptoms) and consultation with a local hepatologist (if applicable; discussed in [Section 11.6.1.1](#)). The local hepatologist is the expert usually consulted by the treating physician for assessment and management of potential hepatic disease. This would usually be a hepatologist, but may be a gastroenterologist. Additional investigation and monitoring may be required and adapted based on the diagnosis after the cause of the liver injury/abnormality is confirmed (details in [Section 11.6.1.4](#)).

The results of all monitoring, including laboratory testing and other testing, should be made available to the study site and sponsor.

All initial tests resulting in abnormal hepatic laboratory values need to be repeated, but appropriate medical action must not be delayed waiting for the repeat result.

If tests are done locally for more rapid results, a concurrent sample should also be sent to the central laboratory whenever possible. Medical care decisions are to be made initially using the most rapidly available results and a conservative approach must be taken if the results from the 2 laboratory tests are significantly different. Data from the local and central laboratory are to be recorded on the applicable eCRF pages.

When IMP is discontinued, all concomitant medications and herbal supplements that are not medically necessary should also be discontinued. In these cases, the investigator should also consider dose reduction for medically necessary concomitant medication and consider changing any medically required concomitant medication known to be hepatotoxic to a suitable alternative.

When IMP is stopped due to PDILI (as described in [Section 6.3.1](#)), IMP must be permanently discontinued unless a subsequent alternative diagnosis fully explains the hepatic findings.

Rechallenge with a substance potentially causing drug-induced liver injury is dangerous, may be fatal, and must not occur.

The table below summarizes the approach to investigate PDILI.

Table 11–3: Required investigations and follow up for PDILI

Laboratory value			Immediate		Follow up	
ALT or AST	Total bilirubin	Symptoms ^a of hepatitis or hypersensitivity	Consultation requirements	Actions	Testing	Evaluation
≥3xULN	≥2xULN ^b	NA	Hepatology consult. ^c	Immediate, permanent IMP discontinuation.	Essential: Must have repeat liver chemistry values and additional testing completed ASAP (see Section 11.6.1.3).	Monitoring of liver chemistry values at least twice per week until values normalize, stabilize, or return to within baseline values. ^d
≥8xULN	NA	NA	Medical Monitor must be notified within 24 hours (eg, by laboratory alert) and subject discussed with Medical Monitor ASAP.			
≥3xULN	NA	Yes		Immediate, temporary or permanent, IMP discontinuation.		
≥3xULN (and ≥2x baseline) and <5xULN	<2xULN	No	Discussion with Medical Monitor required if the criterion that allows for IMP continuation is met.	Further investigation – immediate IMP discontinuation not required (see Section 11.6.1.2).	Not required unless otherwise medically indicated (at discretion of investigator).	
≥5xULN (and ≥2x baseline)	<2xULN	No	Discussion with Medical Monitor required.	Immediate, permanent IMP discontinuation.	Essential: Every attempt must be made to have repeat liver chemistry values and additional testing completed within 48 hours (see Section 11.6.1.3).	Monitoring of liver chemistry values at least twice per week until values normalize, stabilize, or return to within baseline values. ^d

Table 11–3: Required investigations and follow up for PDILI

Laboratory value			Immediate		Follow up	
ALT or AST	Total bilirubin	Symptoms ^a of hepatitis or hypersensitivity	Consultation requirements	Actions	Testing	Evaluation

ALP=alkaline phosphatase; ALT=alanine aminotransferase; ASAP=as soon as possible; AST=aspartate aminotransferase; IMP=investigational medicinal product; NA=not applicable; PDILI=potential drug-induced liver injury; ULN=upper limit of normal

^a Hepatitis symptoms include fatigue, nausea, vomiting, and right upper quadrant pain or tenderness; hypersensitivity symptoms include eosinophilia (>5%), rash, and fever (without clear alternative cause).

^b If the subject also has $\geq 2x$ ULN ALP, the possibility of an indication of biliary obstruction should be discussed with the Medical Monitor.

^c Details provided in [Section 11.6.1.1](#). The local hepatologist is the expert usually consulted by the treating physician for assessment and management of potential hepatic disease. This would usually be a hepatologist, but may be a gastroenterologist.

^d Unless an alternative monitoring schedule is agreed by the investigator and UCB responsible physician. Determination of stabilization is at the discretion of the investigator in consultation with the hepatologist (as applicable) and UCB responsible physician, as needed.

11.6.1.1 Consultation with Medical Monitor and local hepatologist

Potential drug-induced liver injury events require notification of the Medical Monitor within 24 hours (eg, by laboratory alert), and the subject must be discussed with the Medical Monitor as soon as possible. If required, the subject must also be discussed with the local hepatologist. The local hepatologist is the expert usually consulted by the treating physician for assessment and management of potential hepatic disease. This would usually be a hepatologist, but may be a gastroenterologist. If determined necessary, this discussion should be followed by a full hepatology assessment (see [Section 11.6.1.3](#)) and SAE report (if applicable).

11.6.1.2 Immediate action: determination of IMP discontinuation

All PDILI events require immediate action, testing, and monitoring.

The immediate action is dependent on the laboratory values and symptoms of hepatitis or hypersensitivity and ranges from continuation of IMP (followed by immediate investigation) to immediate and permanent discontinuation (see [Section 6.3.1](#) and [Table 11-3](#) for details).

When IMP is discontinued, all concomitant medications and herbal supplements that are not medically necessary should also be discontinued. The investigator should also consider dose reduction for medically necessary concomitant medication and consider changing any medically required concomitant medication known to be hepatotoxic to a suitable alternative.

11.6.1.3 Testing: identification/exclusion of alternative etiology

The measurements and additional information required for the assessment of PDILI events when there is a reasonable possibility that they may have been caused by the IMP are detailed in [Table 11-4](#) (laboratory measurements) and [Table 11-5](#) (additional information). Results of the laboratory measurements and information collected are to be submitted to the sponsor on the corresponding eCRF. If the medical history of the subject indicates a requirement for other assessments not included below, these additional assessments should be completed and submitted, as applicable.

All blood samples should be stored, if possible. If tests are done locally for more rapid results, a concurrent sample must also be sent to the central laboratory.

The following measurements are to be assessed:

Table 11-4: PDILI laboratory measurements

Virology-related	Hepatitis A IgM antibody
	HBsAg
	Hepatitis E IgM antibody
	HBcAb-IgM
	Hepatitis C RNA
	Cytomegalovirus IgM antibody
	Epstein-Barr viral capsid antigen IgM antibody (if unavailable, obtain heterophile antibody or monospot testing)
Immunology	Anti-nuclear antibody (qualitative and quantitative)

Table 11–4: PDILI laboratory measurements

	Anti-smooth muscle antibody (qualitative and quantitative)
	Type 1 anti-liver kidney microsomal antibodies (qualitative and quantitative)
Hematology	Eosinophil count
Urinalysis	Toxicology screen
Chemistry	Amylase
	If total bilirubin $\geq 1.5 \times \text{ULN}$, obtain fractionated bilirubin to obtain % direct bilirubin
	Serum CPK and LDH to evaluate possible muscle injury causing transaminase elevation
Additional	Prothrombin time/INR ^a
	Serum pregnancy test
	PK sample

ALT=alanine aminotransferase; CPK=creatine phosphokinase; HBcAb-IgM=hepatitis B core antibody-IgM; HBsAg=hepatitis B surface antigen; IgM=immunoglobulin M; INR=international normalized ratio; LDH=lactate dehydrogenase; PDILI=potential drug-induced liver injury; PK=pharmacokinetic; RNA=ribonucleic acid; ULN=upper limit of normal

^a Measured only for subjects with ALT $> 8 \times \text{ULN}$, elevations in total bilirubin, and symptoms of hepatitis or hypersensitivity. Hepatitis symptoms include fatigue, nausea, vomiting, and right upper quadrant pain or tenderness; hypersensitivity symptoms include eosinophilia ($> 5\%$), rash, and fever (without clear alternative cause).

The following additional information is to be collected:

Table 11–5: PDILI information to be collected

New or updated information
Concomitant prescription and over-the-counter medications (eg, acetaminophen, herbal remedies, vitamins); dosages and dates should be included.

Pertinent medical history, including the following:
 
 • History of liver disease (eg, autoimmune hepatitis, nonalcoholic steatohepatitis or other “fatty liver disease”) • Adverse reactions to drugs • Allergies • Relevant family history or inheritable disorders (eg, Gilbert’s syndrome, alpha-1 antitrypsin deficiency) • Recent travel • Progression of malignancy involving the liver (Note: Metastatic disease to the liver, by itself, should not be used as an explanation for significant AST and/or ALT elevations.)
The appearance or worsening of clinical symptoms of hepatitis or hypersensitivity (eg, fatigue, nausea, vomiting, right upper quadrant pain or tenderness, decreased appetite, abdominal pain, jaundice, fever, or rash)

Table 11–5: PDILI information to be collected

New or updated information
Recent clinically significant hypotension or hypoxemia with compromised cardiopulmonary function
Alcohol and illicit drug use
Results of liver imaging or liver biopsy, if done
Results of any specialist or hepatology consult, if done
Any postmortem/pathology reports

ALT=alanine aminotransferase; AST=aspartate aminotransferase; PDILI=potential drug-induced liver injury

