11.1.1.3 Adverse events of special interest

An AE of special interest is any AE that a regulatory authority has mandated be reported on an expedited basis, regardless of the seriousness, expectedness, or relatedness of the AE to the administration of a UCB product/compound.

Potential Hy’s Law, defined as $\geq 3 \times \text{ULN}$ ALT or AST with coexisting $\geq 2 \times \text{ULN}$ total bilirubin in the absence of $\geq 2 \times \text{ULN}$ ALP, with no alternative explanation for the biochemical abnormality, must ALWAYS be reported to UCB as an AE of special interest (ie, without waiting for any additional etiologic investigations to have been concluded). Follow-up information should then be reported if an alternative etiology is identified during investigation and monitoring of the subject.

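### The liver-injury testing rules contradict each other: Table 11-3 does not require testing in the one category that may stay on drug, and the INR footnote does not match the Table 11-3 triggers

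*Protocol*

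**What the plan says.** **Testing in general.** Protocol 11.6.1.2 opens with: "All PDILI events require immediate action, testing, and monitoring". It then says that the response "ranges from continuation of IMP (followed by immediate investigation) to immediate and permanent discontinuation". Protocol 11.6.1 adds: "All initial tests resulting in abnormal hepatic laboratory values need to be repeated".

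**Testing by category.** Table 11-3 has five rows. In the fourth, ALT or AST is at least 3xULN (and at least 2x baseline) but below 5xULN, bilirubin is below 2xULN, and there are no symptoms. Section 6.3.1 lets these subjects continue study drug at the investigator's discretion, and no other PDILI category has that option. The Actions cell for this row reads: "Further investigation – immediate IMP discontinuation not required (see Section 11.6.1.2". Its Testing cell reads: "Not required unless otherwise medically indicated (at discretion of investigator". In the first row the same column reads: "Must have repeat liver chemistry values and additional testing completed ASAP (see Section 11.6.1.3".

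**INR.** Table 11-4 lists prothrombin time/INR among the PDILI measurements. Footnote a says it is measured *only* for subjects with ALT >8xULN, "elevations in total bilirubin, and symptoms of hepatitis or hypersensitivity".

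**Potential Hy's Law.** Section 11.1.1.3 defines it as ALT or AST of at least 3xULN with total bilirubin of at least 2xULN, without ALP of at least 2xULN and without another explanation. It has no 8xULN condition and no symptom condition. Such an event "must ALWAYS be reported to UCB as an AE of special interest".

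**The concern.** Two sets of instructions cannot both be followed as written.

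First, the fourth row of Table 11-3 sends the reader to 11.6.1.2 for the action. That section says testing is required for all PDILI events, while the next cell of the same row says it is not required. The subjects concerned are the ones who may still be exposed to study drug.

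Second, the INR footnote combines a restrictive *only* with a three-part condition joined by *and*. It also uses a different analyte and a different inequality from the table that triggers the testing. Depending on how it is read, it can remove INR from events that the protocol singles out for special reporting.

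At stake is whether the same liver event is worked up in the same way each time, and whether the data needed to judge it are collected.

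**Working it through.** The plan states no figure here to reproduce. The check compares the passages and then works through the logic of the footnote.

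**Part 1: the Testing cell**

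| Source (Protocol) | Rule for ALT/AST 3 to <5xULN, bilirubin <2xULN, no symptoms |
|---|---|
| 11.6.1 | Repeat of any abnormal hepatic test is needed |
| 11.6.1.2 | Testing and monitoring for all events; investigation even if drug continues |
| Table 11-3, Actions | Further investigation, citing 11.6.1.2 |
| Table 11-3, Testing | Not required unless medically indicated |

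If the Testing column meant only the aetiology panel of Tables 11-4 and 11-5, the last line could stand beside the others. But the first row, and the fifth row (at least 5xULN), put repeat liver chemistry and additional testing together in that column. Read in the same way, *not required* in the fourth row also covers the repeat that 11.6.1 makes universal.

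**Part 2: the INR footnote**

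With values in multiples of ULN and ALP <2xULN taken as given:

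- Hy's Law laboratory thresholds: max(ALT, AST) ≥ 3 and bilirubin ≥ 2.
- Footnote, all-of reading: ALT > 8 and bilirubin > 1 and symptoms.
- Footnote, any-of reading: ALT > 8 or bilirubin > 1 or symptoms.

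The footnote gives no bilirubin cut-off. Above 1xULN is assumed; any cut-off that includes bilirubin of 2xULN gives the same counts below.

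| ALT | AST | Bilirubin | Symptoms | Hy's Law thresholds | INR, all-of | INR, any-of |
|---|---|---|---|---|---|---|
| 4 | 1 | 3 | no | yes | no | yes |
| 4 | 1 | 3 | yes | yes | no | yes |
| 1 | 10 | 3 | yes | yes | no | yes |
| 10 | 1 | 3 | no | yes | no | yes |
| 10 | 1 | 3 | yes | yes | yes | yes |
| 1 | 10 | 1 | no | no | no | **no** |
| 8 | 1 | 1 | no | no | no | **no** |

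A grid shows how far the two readings differ. ALT and AST are each set at 1, 2, 3, 4, 5, 6, 8, 8.1 and 10; bilirubin at 1, 1.2, 2 and 3; symptoms yes or no.

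- ALT/AST pairs: 9 × 9 = 81. Pairs with both below 3: 2 × 2 = 4. This leaves 77.
- Patterns meeting the Hy's Law thresholds: 77 × 2 bilirubin levels × 2 symptom states = 308.
- Qualifying for INR, all-of: 2 ALT levels × 9 AST levels × 2 bilirubin levels × 1 symptom state = 36. Not qualifying: 308 − 36 = 272.
- Qualifying for INR, any-of: 308, because raised bilirubin alone is enough.

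These counts illustrate the logic. They are not a prevalence.

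The last two lines of the table show what neither reading repairs. Table 11-3 uses ALT *or AST* and *≥8*; the footnote uses ALT alone and *>8*. An isolated AST of 10xULN meets the ≥8xULN row. If it is also at least 2x baseline, it meets the fifth row too, whose own Testing cell is marked *Essential*. It gets no INR on either reading.

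**The case against.** The best defence of the Testing cell is that graded work-up is intended. Section 11.6.1 introduces Table 11-3 by saying that the specific tests depend on laboratory results and symptoms. Section 11.6.1.3 confines the aetiology panel to events that the drug may reasonably have caused. The fourth row is also the mildest category. Read together, the rules could mean repeat chemistry always, monitoring always, and a panel graded by severity. That may well be the intent, and a graded panel is a legitimate design choice. What remains is that the Testing column does not separate the repeat from the panel, so the cell as written overrides a rule stated for all.

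The best defence of the footnote is that its three items mirror the first three rows of Table 11-3 (bilirubin, 8xULN, symptoms), which favours reading them as alternatives. This is a fair argument, and on that reading every potential Hy's Law case qualifies. The mismatches in analyte and inequality remain.

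Three stronger inferences are tempting, and the documents do not support them.

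- *A subject in the fourth row could go untested from Visit 6 (Day 22) to Visit 9 (Day 106), 84 days.* The repeat rule in 11.6.1, follow-up monitoring in 11.6.1.4, the rule in 6.3.1 to stop drug if the monitoring schedule cannot be kept, and Medical Monitor contact (11.6.1.1) all apply between scheduled visits. The blank Evaluation cell in the extracted table is probably a merged cell, so nothing can be drawn from it.
- *The footnote withholds INR from Hy's Law cases outright.* It does so only on the all-of reading, and even then cases with ALT above 8xULN and symptoms qualify.
- *Different sites will apply different rules.* The protocol Summary plans a single remote site, and every PDILI event goes to the Medical Monitor.

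**Conclusion.** The PDILI testing rules are internally inconsistent in two places, and both inconsistencies are in the current protocol text.

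1. The Testing cell for the only category that may continue study drug conflicts with 11.6.1 and 11.6.1.2, and with the section that its own row cites. This assumes that the column has the same scope in every row.
2. Footnote a is ambiguous, with a serious consequence on one reading: potential Hy's Law cases lacking either ALT above 8xULN or symptoms get no INR. On both readings it fails to match Table 11-3 on analyte and inequality, so an isolated AST elevation of 8xULN or more is left out.

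The size is one footnote and one table cell. No claim is made about the length of any monitoring gap or the number of subjects affected. Sample size, error rates and efficacy analyses do not depend on this. SAP 10.3.1 plans only a listing of elevated liver results, and SAP Section 1 says that the study was terminated early, so the benefit within this study may be limited. The change should be made, because it bears on subject safety and costs almost nothing.

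**What to change.** The sponsor must reconcile the passages; which tests apply to which category is for the sponsor to decide.

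- **Table 11-4, footnote a:** align it with the Table 11-3 rows. Use the same analytes and the same inequality, give a bilirubin threshold, and write *any of* or *all of* explicitly.
- **Table 11-3, Testing cell of the 3 to <5xULN row:** reconcile it with 11.6.1 and 11.6.1.2. State the rule for repeat liver chemistry separately from the rule for the aetiology panel.

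The cost is a wording change to one footnote and one cell. Depending on what the sponsor decides, it may mean an occasional extra tube in a rare event for which blood is already being drawn.

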11.6.1.4 Follow-up evaluation

Potential drug-induced liver injury events require follow-up monitoring as described in [Table 11–3](#). Monitoring should continue until liver chemistry values normalize, stabilize, or return to baseline. Determination of stabilization is at the discretion of the investigator in consultation with the hepatologist (as applicable) and UCB responsible physician, as needed.

